10.2 Off Study Criteria

- a) Thirty days after the last dose of the investigational agent.
- b) Death
- c) Lost to follow-up
- d) Withdrawal of consent for any required observations or data submission.
- e) Enrollment onto another COG therapeutic (anti-cancer) study
- f) Patient did not receive protocol treatment after study enrollment

11.0 STATISTICAL AND ETHICAL CONSIDERATIONS

11.1 Sample Size and Study Duration

A minimum of 4 patients will be enrolled in this study if the first two patients develop DLTs at DL1 and DL-1. The projected maximum number of evaluable patients is 24. This includes 6 evaluable patients at each of DL 1-3 and 6 additional evaluable patients in a PK expansion cohort. Therefore, the projected maximum number of patients enrolled into this study allowing for 20% inevaluability is 29, and this number is expected to be accrued over 15-29 months. The study design includes several contingencies that may increase the maximum sample size if all contingencies are needed to estimate the MTD. A maximum of 51 patients may be possible in the unlikely scenario that all dose levels require expansion to 12 patients plus 6 additional patients for pharmacokinetic analysis and a 20% inevaluable rate. The maximum sample size of 51 patients could accrue over 26-51 months.

11.1.1 Amendment #4

The projected maximum number of additional (i.e., in addition to the 18 already enrolled) evaluable patients required to complete the study with this amendment is 12. This includes 6 evaluable patients at DL -2 and 6 additional evaluable patients in a PK expansion cohort. Therefore, the projected maximum number of additional patients enrolled into the study allowing for 30% inevaluability is 18, and this number is expected to be accrued over 9-18 months. The overall study will have an expected maximum of 36 patients.

The study design includes several contingencies that may increase the maximum sample size if all contingencies are needed to estimate the MTD. A maximum of 26 additional patients may be possible in the unlikely scenario that DL-2 requires expansion to 12 patients plus 6 additional patients for pharmacokinetic analysis and a 30% inevaluable rate. The maximum sample size of 26 additional patients could accrue over an additional 13-26 months. The overall study will have an absolute maximum enrollment of 44 patients.

11.2 **Definitions**

11.2.1 Evaluable For Adverse Events

Any patient who receives at least one dose of the study drug(s) or who experiences a dose-limiting toxicity is considered evaluable for Adverse Events. In addition, for the dose-escalation portion during Cycles 1 and 2, patients must receive at least 85% of the prescribed dose of protocol therapy per protocol guidelines in Cycle 1 and 85% of the prescribed dose of protocol therapy in Cycle 2, and must have the appropriate toxicity monitoring studies performed to be considered evaluable for dose limiting toxicity. Patients who do not have DLT and are not considered evaluable for toxicity will be replaced.

11.2.2 Maximum Tolerated Dose

- The MTD will be the maximum dose at which fewer than one-third of patients experience a DLT (See [Section 5.5](#)) during Cycles 1 and 2 of therapy.
- In the unlikely event that two DLTs observed out of 6 evaluable patients are different classes of Adverse Effects (e.g. hepatotoxicity and myelosuppression), AND all of the following conditions are met, expansion of the cohort to 12 patients will be considered:
 - One of the DLTs does not appear to be dose-related
 - The Adverse Effects are readily reversible
 - The study chair, DVL statistician, DVL committee chair or vice chair, and IND sponsor all agree that expansion of the cohort is acceptable

If fewer than 1/3 of patients in the expanded cohort experience dose-limiting toxicities, the dose escalation can proceed.

- The DLTs observed in the pharmacokinetic (PK) expansion cohort will be counted towards the total number of DLTs observed at the MTD during the dose escalation portion of the study. If $\geq 1/3$ of the cohort of patients at the MTD (during the dose escalation plus the PK expansion) experience DLT then the MTD will be exceeded.

11.3 Dose Escalation and Determination of MTD

The rolling six phase 1 trial design will be used for the conduct of this study³⁶. Two to six patients can be concurrently enrolled onto a dose level, dependent upon (1) the number of patients enrolled at the current dose level, (2) the number of patients who have experienced DLT at the current dose level, and (3) the number of patients entered but with tolerability data pending at the current dose level. Accrual is suspended when a cohort of six has enrolled or when the study endpoints have been met.

Dose level assignment is based on the number of participants currently enrolled in the cohort, the number of DLTs observed, and the number of participants at risk for developing a DLT (i.e., participants enrolled but who are not yet assessable for toxicity). For example, when three participants are enrolled onto a dose cohort, if toxicity data is available for all three when the fourth participant entered and there are no DLTs, the dose is escalated and the fourth participant is enrolled to the subsequent dose level. If data is not yet available for one or more of the first three participants and no DLT has been observed, or if one DLT has been observed, the new participant is entered at the same dose level. Lastly, if two or more DLTs have been observed, the dose level is de-escalated. This process is repeated for participants five and six. In place of suspending accrual after every three participants, accrual is only suspended when a cohort of six is filled. When participants are inevaluable for toxicity, they are replaced with the next available participant if escalation or de-escalation rules have not been fulfilled at the time the next available participant is enrolled onto the study.

The following table provides the decision rules for enrolling a patient at (i) the current dose level (ii) at an escalated dose level, (iii) at a de-escalated dose level, or whether the study is suspended to accrual:

# Pts Enrolled	# Pts with DLT	# Pts without DLT	# Pts with Data Pending	Decision
2	0 or 1	0, 1 or 2	0, 1 or 2	Same dose level
2	2	0	0	De-escalate*
3	0	0, 1 or 2	1, 2 or 3	Same dose level
3	1	0, 1 or 2	0, 1 or 2	Same dose level
3	0	3	0	Escalate**
3	≥ 2	0 or 1	0 or 1	De-escalate*
4	0	0, 1, 2 or 3	1, 2, 3 or 4	Same dose level
4	1	0, 1, 2 or 3	0, 1, 2 or 3	Same dose level
4	0	4	0	Escalate**
4	≥ 2	0, 1 or 2	0, 1 or 2	De-escalate*
5	0	0, 1, 2, 3 or 4	1, 2, 3, 4 or 5	Same dose level
5	1	0, 1, 2, 3 or 4	0, 1, 2, 3 or 4	Same dose level
5	0	5	0	Escalate**
5	≥ 2	0, 1, 2 or 3	0, 1, 2 or 3	De-escalate*
6	0	0, 1, 2, 3, or 4	2, 3, 4, 5 or 6	Suspend

6	1	0, 1, 2, 3 or 4	0, 1, 2, 3 or 4	Suspend
6	0 or 1	5 or 6	0 or 1	Escalate**
6	≥ 2	0, 1, 2, 3 or 4	0, 1, 2, 3 or 4	De-escalate*

* If six patients already entered at next lower dose level, the MTD has been defined.

** If final dose level has been reached, the recommended dose has been reached.

If two or more of a cohort of up to six patients experience DLT at a given dose level, then the MTD has been exceeded and dose escalation will be stopped (see [Section 11.2.2](#) for exception to rule).

In addition to determination of the MTD, a descriptive summary of all toxicities will be reported.

11.3.1 Amendment #4

Patients will be enrolled at DL -2 using the rolling 6 study design. If DL -2 is determined to be safe (at most 1 out of 6 evaluable patients with DLT), then up to 6 more patients will be enrolled at DL -2 in a PK expansion cohort. If DL -2 is determined to not be tolerable (2 or more dose limited patients out of 6 evaluable patients), the study will be closed to accrual.

11.4 **Inclusion of Children, Women and Minorities**

The study is open to all participants regardless of gender or ethnicity. Review of accrual to past COG studies of new agents demonstrates the accrual of both genders and all NIH-identified ethnicities to such studies. Efforts will be made to extend the accrual to a representative population, but in a Phase 1 trial which will accrue a limited number of patients, a balance must be struck between patient safety considerations and limitations on the number of individuals exposed to potentially toxic or ineffective treatments on the one hand and the need to explore gender, racial, and ethnic aspects of clinical research on the other. If differences in outcome that correlate to gender, racial, or ethnic identity are noted, accrual may be expanded or additional studies may be performed to investigate those differences more fully.

The gender and minority distribution of the study population is projected to be¹:

Racial Categories	Ethnic Categories				Total
	Not Hispanic or Latino		Hispanic or Latino		
	Female	Male	Female	Male	
American Indian/ Alaska Native	0	0	0	0	0
Asian	1	1	0	0	2
Native Hawaiian or Other Pacific Islander	0	0	0	0	0
Black or African American	2	4	0	0	6
White	9	14	4	1	28
More Than One Race	0	0	0	0	0
Total	12	19	4	1	36

PHS 398 / PHS 2590 (Rev. 08/12 Approved Through 8/31/2015) OMB No. 0925-0001/0002

11.5 Pharmacokinetic and Correlative Studies and Response Analysis

A descriptive analysis of pharmacokinetic (PK) parameters of ABI-009 as a single agent and in combination with temozolomide and irinotecan will be performed to define systemic exposure, drug clearance, and other pharmacokinetic parameters. The PK parameters will be summarized with simple summary statistics, including means, medians, ranges, and standard deviations (if numbers and distribution permit).

While the primary aim of this study is to evaluate the toxicity of ABI-009, patients will have disease evaluations performed as indicated in [Section 8.1](#). Disease response will be assessed according to RECIST criteria for patients with solid tumors, and will be reported descriptively.

All these correlative biology study analyses will be descriptive and exploratory and hypotheses generating in nature.

¹These distributions are based on historical Phase 1 enrollments.

12.0 EVALUATION CRITERIA

12.1 Common Terminology Criteria for Adverse Events (CTCAE)

The descriptions and grading scales found in the NCI Common Terminology Criteria for Adverse Events (CTCAE) version 5.0 will be utilized for AE reporting. All appropriate treatment areas should have access to a copy of the current CTCAE version 5.0. A copy of the CTCAE version 5.0 can be downloaded from the CTEP website (http://ctep.cancer.gov/protocolDevelopment/electronic_applications/ctc.htm).

12.2 Response Criteria for Patients with Solid Tumors

See the table in [Section 8.0](#) for the schedule of tumor evaluations. In addition to the scheduled scans, a confirmatory scan should be obtained on the next consecutive cycle following initial documentation of objective response.

Response and progression will be evaluated in this study using the revised Response Evaluation Criteria in Solid Tumors (RECIST) guideline (version 1.1).³⁷ Key points are that 5 target lesions are identified and that changes in the *largest* diameter (unidimensional measurement) of the tumor lesions but the *shortest* diameter of malignant lymph nodes are used in the RECIST v 1.1 criteria.

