2.4.1 Prior Experience in Children

There have been no pediatric studies of ABI-009.

2.5 **Overview of Proposed Pediatric Study**

We propose to conduct a Phase 1 study of ABI-009 in children with relapsed/refractory solid tumors using the rolling 6 design. Cycle 1 will aim to establish tolerability and safety and to

obtain pharmacokinetics of ABI-009 as a single agent dosed on days 1 and 8 of a 21-day cycle. Additionally, Cycle 2+ will aim to determine the MTD and/or RP2D of ABI-009 in combination with temozolomide and irinotecan. The ABI-009 starting dose will be 35 mg/m² as a single agent during Cycle 1, while Cycle 2+ dosing and scheduling in combination with irinotecan (90 mg/m²) and temozolomide (125 mg/m²) will mimic the Phase 1 pediatric trial ADVL0918.²³

2.6 Rationale for Amendment #4 (Addition of Dose Level -2 and modification of the definition of hematological DLT)

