5.0 TREATMENT PROGRAM

5.1 Overview of Treatment Plan

Cycle 2+ Combination Therapy 21 Day Duration					
Day -2	Cefixime				PJP Prophylaxis
Day -1					
Day 1		TEMO	IRIN	ABI-009	
Day 2		TEMO	IRIN		
Day 3		TEMO	IRIN		
Day 4		TEMO	IRIN		
Day 5		TEMO	IRIN		
Day 6					
Day 7					
Day 8				ABI-009	
Day 9-19					
Day 20 ¹	Cefixime				
Day 21 ²		Evaluation			

TEMO: Temozolomide
 IRIN: Irinotecan
 PJP: Pneumocystis pneumonia

¹ Day 20 equals Day -2 of the following cycle.

² Day 21 equals Day -1 of the following cycle.

A cycle of therapy is considered to be 21 days. A cycle may be repeated for a total of 35 cycles, up to a total duration of therapy of approximately 24 months.

Drug doses should be adjusted based on the BSA calculated from height and weight measured within 7 days prior to the beginning of each cycle.

5.1.1 Cycle 1

Pre-Amendment #4: ABI-009 will be administered intravenously over 30 minutes on Days 1 and 8 of Cycle 1 (beginning at Dose Level 1 = 35 mg/m²/dose; see dose escalation table in [Section 5.3.1](#)). The use of in-line filters is NOT necessary. Upon completion of infusion, the infusion catheter should be flushed with normal saline.

Amendment #4: ABI-009 will be administered intravenously over 30 minutes on Days 1 and 8 of Cycle 1 (beginning at Dose Level -2 = 15 mg/m²/dose; see dose escalation table in [Section 5.3.1](#)). The use of in-line filters is NOT necessary. Upon completion of infusion, the infusion catheter should be flushed with normal saline.

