Amylase, Lipase	X	Prior to Cycle 2	X
Pregnancy Test ²	X		
Tumor Disease Evaluation	X	End of Cycles 1 ¹² & 2	Every other cycle x 2 then q 3 cycles ⁵
Bone Marrow Evaluation ⁷	X		
Medication Diary ⁶		Cycle 2	X
Oxygen Saturation	X	Weekly	X ⁸
Tumor Tissue Studies ⁹	X		

[^] Studies may be obtained within 72 hours prior to the start of the subsequent cycle.

¹ See [Section 8.3](#) for timing of PK studies.

² Women of childbearing potential require a negative pregnancy test prior to starting treatment; sexually active patients must use an acceptable method of birth control. Abstinence is an acceptable method of birth control.

³ If patients have Grade 4 neutropenia then CBCs should be checked at least every 2-3 days until recovery to Grade 3 or until meeting the criteria for dose limiting toxicity.

⁴ If patients develop Grade 4 neutropenia or Grade 4 thrombocytopenia then CBCs should be checked every 3 to 4 days until recovery to Grade 3

⁵ Tumor Disease Evaluation should be obtained on the next consecutive cycle after initial documentation of either a PR or CR. Subsequent scans may restart 2 cycles after the confirmatory scan. Please note that for solid tumor patients, if the institutional investigator determines that the

- patient has progressed based on clinical or laboratory evidence, he/she may opt not to confirm this finding radiographically.
- ⁶ Medication diary (see [Appendix IX](#)) should be reviewed after completion of each treatment cycle and uploaded into RAVE.
- ⁷ As appropriate for disease, to confirm bone marrow involvement at enrollment, or as clinically indicated.
- ⁸ Required prior to each cycle; weekly for subsequent cycles only if clinically indicated.
- ⁹ See [Section 8.4](#) and [Appendix XII](#) for details of Tumor Tissue studies.
- ¹⁰ If Grade 3 or 4 hypercholesterolemia or Grade 3 or 4 hypertriglyceridemia is detected when routine (non-fasting) laboratory studies are performed, the tests should be repeated within 3 days in the fasting state to permit accurate grading.
- ¹¹ If the initial blood glucose is a random sample that is outside of the normal limits, then follow-up fasting blood glucose can be obtained and must be within the upper normal limits for age. If blood glucose is $\geq 250 - 500$ mg/dL or $> 13.9 - 27.8$ mmol/L when routine (non-fasting) laboratory studies are performed, the test should be repeated within 3 days in the fasting state to permit accurate grading.

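### For measurable solid tumors the designated confirmatory scan falls nominally 21 days after first response, short of Table 1's 28-day minimum, and the 12.7.1 table codes prior stable disease or response as progression

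*Combined protocol and SAP*

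**What the plan says.** **Scan schedule.** Section 5.1: "A cycle of therapy is considered to be 21 days". Its footnote adds that "Day 21 equals Day -1 of the following cycle", so Day 22 is Day 1 of the next cycle. The Section 8.1 table schedules the first two tumor evaluations at "End of Cycles 1 ¹² & 2". Footnote 5 continues: "Tumor Disease Evaluation should be obtained on the next consecutive cycle after initial documentation of either a PR or CR", and then "Subsequent scans may restart 2 cycles after the confirmatory scan". Section 12.2 repeats the confirmatory rule: "a confirmatory scan should be obtained on the next consecutive cycle following initial documentation of objective response". A note to the 8.1 table says "Studies may be obtained within 72 hours prior to the start of the subsequent cycle"; it is attached to the column for subsequent cycles.

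**Table 1 (Section 12.2.5, measurable disease).** The best-response column asks for confirmation at 28 days or more. It credits stable disease documented once, at 28 days or more from baseline. It assigns PD only where no SD, PR or CR came before.

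**Section 12.7.1.** The text defines best overall response as the best one recorded up to progression or recurrence, and makes it depend on confirmation as well as measurement. The table below it pairs a first and a second assessment. SD, PR or CR followed by progression becomes progressive disease. SD with no second assessment becomes unclassifiable. The table gives no interval between the two assessments.

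**The concern.** The plan names one scan as the confirming scan and, for measurable solid tumors, sets a minimum interval which that scan does not reach on schedule. A responder imaged exactly as instructed stays unconfirmed under Table 1. If that patient then progresses or stops before the next scan, the response is never confirmed.

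The 12.7.1 table adds a separate conflict. A patient with qualifying stable disease who later progresses is SD under Table 1 and under the 12.7.1 definition, but PD in the 12.7.1 table. Two analysts who both follow the protocol could report different best responses for the same patient.

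**Working it through.** **Cycle length.** Section 5.1 allows 35 cycles over about 24 months. 35 × 21 = 735 days, and 735 / 30.44 = 24.1 months. The stated duration is reproduced, so 21 days is the right input.

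**Interval to the designated scan, no cycle delay**
- Nominal: 21 days.
- 72-hour window assumed for both scans: first scan on Days 19-22, second on Days 40-43. Shortest 40 − 22 = 18 days; longest 43 − 19 = 24 days.
- First scan fixed on Day 21: 40 − 21 = 19 to 43 − 21 = 22 days.

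All are below 28. Applying the window to the end-of-Cycle-1 and end-of-Cycle-2 scans is an assumption, because the note belongs to another column.

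**Cycle delay needed to reach 28 days.** Nominal 28 − 21 = 7 days. With the window, 28 − 24 = 4 to 28 − 18 = 10 days.

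**Next scan after the designated one.** Two cycles later it falls on Days 82-85: 82 − 22 = 60 to 85 − 19 = 66 days after first response (nominal 3 × 21 = 63).

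**Best-response codes side by side**

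| Sequence | 12.7.1 table | Table 1 and 12.7.1 text |
|---|---|---|
| SD, then progression | PD | SD, if documented ≥ 28 days from baseline |
| PR or CR, then progression | PD | Not PD in Table 1; PR or CR only if confirmed |
| SD, then not done | Unclassifiable | SD in Table 1, if documented ≥ 28 days from baseline |
| SD-SD, PR-PR, PR-CR, CR-CR | SD, PR, PR, CR | Same, if the confirmation interval is met |

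**When end-of-Cycle-1 SD qualifies.** That scan falls 18-21 days after Day 1. Baseline imaging must therefore precede Day 1 by at least 28 − 21 = 7 to 28 − 18 = 10 days. Section 4.0 allows up to 14 days, so some patients qualify and others do not.

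**Size of one recoded patient** (Section 11.1.1 gives an expected maximum enrollment of 36 and an absolute maximum of 44)
- 1/36 = 2.8 points; 1/44 = 2.3 points.
- These counts include CNS and non-measurable disease. The number with measurable solid tumors is not given. As an illustration only, if 12 patients at Dose Level -2 were all response-evaluable and reported alone, 1/12 = 8.3 points.

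**The case against.** **The scan rules are loose.** Sections 8.1 and 12.2 say what should happen and name no day. Cycles may be delayed, and a later routine scan could confirm. This stands to the extent that confirmation is not impossible. But it would then depend on a delay, or on the patient staying on treatment until about Day 82, rather than on the scan the plan designates.

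**Table 1 is damaged in extraction.** The 28-day text is printed on the first two rows. Its extension to the ordinary PR row is inferred from what is probably a merged cell. If the cell is not merged, the timing conflict covers only those two rows. The progression-row conflict with the 12.7.1 definition does not depend on this.

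**Four stronger readings are tempting, and the documents do not support them.**
- That 12.7.1 accepts the 21-day scan outright. Its text refers to confirmation criteria, and the only interval given for confirming a response in measurable solid tumors is Table 1's 28 days. Whether 12.7.1 imports it is unclear.
- That SD followed by a later-confirmed PR is fixed as stable because the table has two columns. Section 12.2.6 speaks of a sequence of assessments, so a pairwise reading over all scans is more natural. This needs clarifying and is not an error.
- That SD followed by no scan always conflicts with Table 1. It does so only when that SD was documented at least 28 days from baseline.
- That no best-response rule exists because five sections cite a missing Section 12.8. The contents list shows Best Response at 12.7, so the references are clerical slips.

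**Response is descriptive.** Section 11.5 sets no threshold or test. This stands and limits the importance of the point, but a descriptive rate still needs one definition.

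**Conclusion.** Two conflicts hold. First, for measurable solid tumors, the designated confirmatory scan comes nominally 21 days after first response (18-24 days if the window is assumed for both scans) against a 28-day minimum. It cannot confirm a response under Table 1 without a cycle delay of about 4-10 days. How far this reaches ordinary PR depends on the merged-cell reading. Second, the 12.7.1 table assigns PD after SD, PR or CR, contrary to Table 1 and to its own definition. The conflict over SD with no further scan is conditional on the 28 days from baseline.

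The timing conflict can change the confirmed response rate. The progression row moves patients into PD who would otherwise be SD or carry an unconfirmed response, and leaves the confirmed response rate as it is. One recoded patient shifts a whole-study rate by about 2.3-2.8 points over 36-44 enrolled, and by more over the smaller number with measurable disease. Only the secondary aim in 1.2.1 is touched; MTD, DLT and sample size are not.

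**What to change.** 1. Reconcile Table 1 with Sections 8.1 and 12.2. The simplest way is to set the minimum confirmation interval to the scheduled next-cycle scan including its window, and to state that window for the tumor evaluations. The price is an interval shorter than 28 days. The alternative is to keep 28 days and time the scan accordingly, which takes it off the cycle schedule.
2. State which rows of Table 1 the interval covers, and that 12.7.1 uses the same interval.
3. Amend the 12.7.1 table. Assign PD only when no SD, PR or CR meeting its criteria came before. Let a confirmed CR or PR, or a qualifying SD, keep its code when progression or no further scan follows. Let any two consecutive assessments before progression confirm a response. State the code for an unconfirmed PR or CR.
4. Apply the one rule to all patients, including the 18 already enrolled.
5. Correct the five references from 12.8 to 12.7, and the reference in 12.4.5 to a Table 3 there (clerical).

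The cost is wording plus coding the enrolled patients under the chosen rule. No new scans are needed if the interval follows the existing schedule.
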